- a. This telephone contact should occur approximately 6 months after study vaccination; this contact should be attempted for all participants who have received study vaccination, unless the parents/legal guardians have withdrawn consent.
- b. For Cohorts 1 and 2, information on the prior vaccination with 13vPnC will also be recorded. For Cohorts 3 and 4, information on prior vaccination with 7vPnC or 13vPnC will be recorded, if available. See [Section 6.5.3](#) for details.
- c. Record only concomitant medications used to treat SAEs and NDCMCs.
- d. The investigator or designee will inform the participant of the need to use highly effective contraception consistently and correctly until 28 days after the dose of investigational product and document the conversation and the participant's affirmation in the source notes.
- e. For Cohorts 1 and 2: ~5 mL; for Cohorts 3 and 4: ~10 mL.
- f. Blood sample will be collected prior to vaccination.
- g. Remind the participant's parent(s)/legal guardian(s) that the use of prophylactic antipyretic/pain medication, while permitted, is not recommended on the day of investigational product administration (before or after vaccination).
- h. Administer permitted routine pediatric vaccinations (as applicable) after the investigational product into a limb other than the site of the 20vPnC injection. Prohibited and permitted vaccines are described in Sections [6.5.1](#) and [6.5.2](#), respectively.
- i. The participant's parent(s)/legal guardian(s) will record prompted local reactions and systemic events and antipyretic/pain medication in an e-diary for the 7 days following vaccination. The participant's parent(s)/legal guardian(s) will be instructed to contact the study staff if the participant experiences severe redness or swelling >14 caliper units, severe pain at the injection site (left leg [option for Cohort 1 only] or left arm), a fever >40.0°C (>104.0°F), or an emergency room visit or hospitalization.
- j. Designated site staff will review e-diary data online at frequent intervals (daily is optimal) for the 7 days following vaccination to evaluate participant compliance and as part of the ongoing safety review.
- k. An NDCMC is defined as a disease or medical condition, not previously identified, that is expected to be persistent or otherwise long-lasting in its effects.

PFIZER CONFIDENTIAL

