5.2. Exclusion Criteria

[figure not shown]
[figure not shown]
Participants are excluded from the study if any of the following criteria apply:

5.2.1. Cohort 1 and Cohort 2

Medical Conditions:

1. History of severe adverse reaction associated with a vaccine and/or severe allergic reaction (eg, anaphylaxis) to any component of the investigational product, or any diphtheria toxoid-containing vaccine.
2. Significant neurological disorder or history of seizure (excluding febrile seizure) or significant stable or evolving disorders such as cerebral palsy, encephalopathy, hydrocephalus, or other significant disorders.
3. Major known congenital malformation or serious chronic disorder.
4. History of microbiologically proven invasive disease caused by *S pneumoniae*.
5. Known or suspected immunodeficiency or other conditions associated with immunosuppression, including, but not limited to, immunoglobulin class/subclass deficiencies, DiGeorge syndrome, generalized malignancy, human immunodeficiency virus (HIV) infection, leukemia, lymphoma, or organ or bone marrow transplant.
6. Bleeding diathesis or condition associated with prolonged bleeding that would, in the opinion of the investigator, contraindicate intramuscular injection.
7. Congenital, functional, or surgical asplenia.
8. Other acute or chronic medical or psychiatric condition including recent (within the past year) or active suicidal ideation or behavior or laboratory abnormality that may increase the risk associated with study participation or investigational product administration or may interfere with the interpretation of study results and, in the judgment of the investigator, would make the participant inappropriate for entry into this study.

PFIZER CONFIDENTIAL

Prior/Concomitant Therapy:

9. Previous vaccination with any investigational pneumococcal vaccine or with PPSV23, or planned receipt through study participation.
10. Currently receives treatment with immunosuppressive therapy, including cytotoxic agents or systemic corticosteroids, or planned receipt through the last blood draw. If systemic corticosteroids have been administered short term (<14 days) for treatment of an acute illness, participants should not be enrolled into the study until corticosteroid therapy has been discontinued for at least 28 days before investigational product administration. Inhaled/nebulized, intra-articular, intrabursal, or topical (skin, eyes, or ears) corticosteroids are permitted.

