11. Receipt of blood/plasma products or immunoglobulins (including hepatitis B immunoglobulin) or planned receipt through the last planned blood draw in the study (through Visit 2).

Prior/Concurrent Clinical Study Experience:

12. Participation in other studies involving investigational drug(s), investigational vaccines, or investigational devices within 28 days prior to study entry and/or during study participation. Participation in purely observational studies is acceptable.

Diagnostic Assessments:

Not applicable.

Other Exclusions:

[figure not shown]
13. Children or grandchildren who are direct descendants of investigator site staff members or Pfizer employees who are directly involved in the conduct of the study.

5.2.2. Cohort 3 and Cohort 4

Medical Conditions:

1. History of severe adverse reaction associated with a vaccine and/or severe allergic reaction (eg, anaphylaxis) to any component of the investigational product, or any diphtheria toxoid-containing vaccine.
2. Significant neurological disorder or history of seizure (excluding febrile seizure) or significant stable or evolving disorders such as cerebral palsy, encephalopathy, hydrocephalus, or other significant disorders.
3. Major known congenital malformation or serious chronic disorder.

PFIZER CONFIDENTIAL

4. History of microbiologically proven invasive disease caused by *S pneumoniae*.
5. Known or suspected immunodeficiency or other conditions associated with immunosuppression, including, but not limited to, immunoglobulin class/subclass deficiencies, DiGeorge syndrome, generalized malignancy, HIV infection, leukemia, lymphoma, or organ or bone marrow transplant.
6. Bleeding diathesis or condition associated with prolonged bleeding that would, in the opinion of the investigator, contraindicate intramuscular injection.
7. Congenital, functional, or surgical asplenia.
8. Other acute or chronic medical or psychiatric condition including recent (within the past year) or active suicidal ideation or behavior or laboratory abnormality that may increase the risk associated with study participation or investigational product administration or may interfere with the interpretation of study results and, in the judgment of the investigator, would make the participant inappropriate for entry into this study.
9. Pregnant or breastfeeding female participants.

Prior/Concomitant Therapy:

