6.5.1. Prohibited Concomitant Vaccines and Treatments

- Receipt of any investigational vaccines, drugs, or medical devices is prohibited during study participation.
- Receipt of nonstudy pneumococcal vaccine is prohibited during study participation.
- Receipt of blood/plasma products, immunoglobulins, and/or immunosuppressive therapy (including a ≥ 14 -day course of systemic corticosteroids) is prohibited through Visit 2.

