6.5.3. Recording Prior and Concomitant Vaccines and Treatments

The name, location, and date of administration for any nonstudy vaccinations received from the time of signing of the ICD to Visit 2 will be collected and recorded in the CRF.

For Cohorts 1 and 2, confirmation in the source documents of 3 or more prior doses of 13vPnC with the date of administration of the most recent (third or fourth) dose of 13vPnC is to be recorded on the CRF. For Cohorts 3 and 4, the date of administration of the most recent dose of 7vPnC or 13vPnC will be recorded on the CRF, if available.

Only medications taken to treat SAEs or NDCMCs from the time of signing of the ICD to the final visit (approximately 6 months after vaccination at Visit 1) will be collect and recorded in the CRF.

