3.4.3. Prior/Concomitant Vaccines and Concomitant Medications

Specific prior and concomitant vaccines will be collected as indicated in the protocol and recorded in the CRF. Concomitant medications will be recorded only if they are used to treat SAEs and NDCMCs. Concomitant and prior vaccines and concomitant medications will be coded using WHO DDE.

Participants' age at the time of their last 13vPnC or 7vPnC vaccination will be categorized as <1 year of age or ≥ 1 year of age. Additionally, time since the last 13vPnC or 7vPnC vaccination will be categorized in the following intervals: 2 to <6 months, 6 to <12 months, 1 to <5 years, 5 to <10 years, and 10 years or more.

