4. ANALYSIS SETS (POPULATIONS FOR ANALYSIS)

Analysis populations are defined for the statistical analysis of safety and immunogenicity results in the table below.

Population	Description
Enrolled	All participants who have a signed ICD.
Evaluable immunogenicity	All participants who: 1. Are eligible, 2. Receive 20vPnC, 3. Have at least 1 valid immunogenicity result from 1 month after vaccination collected within 27 to 56 days after vaccination for Cohorts 1-2 or within 27 to 49 days after vaccination for Cohorts 3-4, and 4. Have no other major protocol deviations as determined by the clinician The evaluable immunogenicity population will be used as the primary analysis population for the pneumococcal immunogenicity results.
CCI	[REDACTED]
Safety	All participants who receive 20vPnC and have safety follow-up after vaccination.

PFIZER GENERAL BUSINESS

[REDACTED]

For the evaluable immunogenicity population definition, the blood collection window has been expanded by 1 extra day before and 14 days after the protocol-specified blood collection window of 28 to 42 days, for consistency with established rules in the Prevnar 13® development program for Cohorts 1 and 2. For Cohorts 3 and 4, the window was expanded by 1 day before and 7 days after the protocol-specified blood collection window consistent with the 20vPnC adult program. A major protocol deviation is a protocol deviation that, in the opinion of the Pfizer clinician or medical monitor, would materially affect assessment of immunogenicity, eg, participant receipt of a prohibited vaccine or medication that might affect immune response or a medication error with suspected decrease in potency of the vaccine.

CC1

E-diary data will be summarized among those in the safety population who report any e-diary data.

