6.5.4. Concomitant Medications and Nondrug Treatments

Each prior/concomitant vaccine will be summarized according to the ATC fourth-level classification. The number and percentage of enrolled participants receiving concomitant vaccines will be summarized according to cohort.

Concomitant medications used to treat SAEs and NDCMCs will be summarized for the time of vaccination to 6 months after vaccination (safety population).

A categorical summary of participants' age at the time of their last 13vPnC or 7vPnC vaccination will be done. Participants will be categorized as <1 year of age or ≥ 1 year of age. Additionally, time since the last 13vPnC or 7vPnC vaccination will be summarized in the categories shown in [Section 3.4.3](#).

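### Does limiting the medication record to drugs for SAEs and NDCMCs leave the prohibited-medication exclusion unworkable?

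*Protocol*

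**What the plan says.** Protocol 6.5.1 prohibits "Receipt of blood/plasma products, immunoglobulins, and/or immunosuppressive therapy" through Visit 2; a systemic corticosteroid course of 14 days or more counts as immunosuppressive therapy.

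The medication record is narrower, and the limit is the same throughout:

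- Protocol 6.5.3: "Only medications taken to treat SAEs or NDCMCs from the time of signing of the ICD to the final visit" are collected.
- Schedule of Activities, footnote c: "Record only concomitant medications used to treat SAEs and NDCMCs".
- SAP 3.4.3: "Concomitant medications will be recorded only if they are used to treat SAEs and NDCMCs".
- SAP 6.5.4: "Concomitant medications used to treat SAEs and NDCMCs will be summarized".

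Nonstudy vaccines are handled differently. Protocol 6.5.3 has all of them recorded, with name and date, from consent to Visit 2.

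SAP section 4 requires a child in the evaluable immunogenicity population to be eligible and to have no other major protocol deviation in the clinician's judgment. One example it gives of a major deviation is "participant receipt of a prohibited vaccine or medication that might affect immune response".

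**The concern.** Set side by side, the two rules do not match. The exclusion covers prohibited vaccines and prohibited medications. The vaccine half can be applied from recorded data. The medication half has a matching record only when the drug treats an SAE or NDCMC. A 14-day steroid course for a nonserious illness, or immunoglobulin given as prophylaxis, falls outside the listing. For steroids the prohibition also depends on duration, so dates are needed to apply it.

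The evaluable population carries the primary GMFR tests. Its estimand describes the response in children who follow the protocol. If prohibited treatment is noticed at some sites and not at others, membership of that population is uneven, and children with an altered response could stay in the primary analysis.

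**Working it through.** **Does anything other than the medication listing bring these treatments to light?**

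| Route | What it covers |
|---|---|
| Protocol 5.2, entry criteria | Current immunosuppressive therapy "or planned receipt through the last blood draw"; receipt of blood products or immunoglobulins, or "planned receipt through the last planned blood draw in the study (through Visit 2") |
| Protocol 6.5.3 | Treatments for SAEs and NDCMCs, recorded directly |
| Protocol 8.3.1.2 and 8.3.3 | Nonserious AEs through Visit 2 are on the CRF, and follow-up of an event must supply relevant information, with concomitant medications named as an example |
| Protocol 10.3.1 | A flare of a pre-existing condition is itself an AE, so steroids for a flare fall under the previous row |
| Schedule of Activities and 8.10.2 | Documented check of continued eligibility at Visit 2 |
| SAP section 4 | Clinician judgment on deviations, not tied to the medication listing |

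What remains is mainly unplanned use without a reported AE, in children who were healthy at entry, over the 28 to 42 days between visits.

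**How much could that matter?** Cohorts 1 and 2 have more than 99% power for every serotype (Protocol Table 6). The sensitive case is OPA 11A in Cohorts 3 and 4. SAP 3.2 has the 7 additional serotypes assayed in all children in those cohorts, so n = 180 applies.

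*Step 1: reproduce Table 6.* The test is a one-sample t-test on the log fold rise, two-sided 0.05. Power is P(T > t(0.975, n−1)), with T noncentral t and noncentrality d√n, where d = mean ln rise / SD.

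- Assumption 1 (75% of the adult GMFR, n = 90, power 64%) gives d = 0.2471.
- The same d at n = 180 gives 90.9%, against 91% in Table 6.
- Assumption 2 (100% of the adult GMFR, n = 90, power 95%) gives d = 0.3842.

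*Step 2: recover the scale.* The two assumptions differ by ln(4/3) = 0.2877 in the mean, with the same SD.

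- SD = 0.2877 / (0.3842 − 0.2471) = 2.10 (2.00 to 2.20 allowing for rounding in Table 6).
- Mean ln rise at 75% = 0.2471 × 2.10 = 0.518, a GMFR of 1.68.

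*Step 3: add undetected treated children.* Let a share f have zero rise. The mean becomes (1 − f) × 0.518 and the variance 2.10² + f(1 − f) × 0.518². The documents give no value for f, so the shares below are assumed.

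| f | Power, kept (n = 180) | Power, excluded | Difference (points) | GMFR ratio |
|---|---|---|---|---|
| 1/180 | 90.6% | 90.8% (n = 179) | 0.2 | 0.997 |
| 1% | 90.4% | 90.6% (n = 178) | 0.3 | 0.995 |
| 2% | 89.8% | 90.3% (n = 176) | 0.5 | 0.990 |

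Differences are taken before rounding. If the 1% had half the usual log rise, power would be 90.66% with them kept and 90.63% with them excluded, so excluding them gains nothing. For 33F, 98% at n = 90 gives d = 0.4277; with d multiplied by 0.99, power at n = 180 is 99.99%.

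*Step 4: direction.* A blunted response pulls the GMFR toward 1, which works against declaring superiority. An immunoglobulin or plasma product could in principle push the other way. The standard error of the mean ln rise is 2.10/√180 = 0.156. To shift the mean by one standard error, 2% of children (3.6 of 180) would each need an excess of 0.156 × 180 / 3.6 = 7.8 natural-log units, which is more than 2,000-fold.

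**The case for a change.** The best case for a change is traceability, not power. A stated exclusion should rest on data gathered the same way at every site, and the later checks are general. The Visit 2 eligibility step points to Section 7.2, which lists only broad withdrawal reasons. The blood-draw delay criterion at that visit concerns antibiotics. AE follow-up starts only once an event is reported, and source verification mainly confirms what was entered. One added question at Visit 2, with name and dates, would need no extra visit or sample.

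Part of this stands. The medication record is narrower than the exclusion rule, and the same limit in both documents shows it was deliberate. It does not follow that the rule has no data behind it. The CRF and the monitoring plan, which Protocol 10.1.6 says covers noncompliance, are outside the documents and may already capture these treatments. Sites have the prohibited list in 6.5.1, and the entry criteria name the same classes of treatment. Recording a Visit 2 answer is a reasonable traceability preference if the CRF lacks it, but the analysis does not depend on it.

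**Conclusion.** No change is needed. The protocol and SAP do not contradict each other: one limits routine medication listing, and the other gives an example to guide a clinician's judgment on deviations. The remaining gap is a missing detail that ordinary deviation review can fill, and closing it would gain almost nothing. In the most sensitive primary test the cost is 0.2 to 0.5 percentage points of power and 0.3% to 1.0% of the GMFR, with 0.5% to 2% of children assumed undetected and wholly unresponsive; with half the usual log rise in 1%, there is no cost. These figures rest on the Table 6 assumptions at n = 180 and on assumed shares, since the true number of undetected cases cannot be derived from the documents. Missed cases with a blunted response would make the superiority claim harder to reach, so the primary conclusions remain sound with the plan as written.

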6.6. Dose Modification

Not applicable.

6.7. Intervention After the End of the Study

No intervention will be provided to study participants at the end of the study.

7. DISCONTINUATION OF STUDY INTERVENTION AND PARTICIPANT DISCONTINUATION/WITHDRAWAL

7.1. Discontinuation of Study Intervention

Since this is a single-dose study, this section is not applicable.

7.2. Participant Discontinuation/Withdrawal From the Study

A participant may be withdrawn from the study at any time at the request of his/her own parent(s)/legal guardian(s), or may be withdrawn at any time at the discretion of the investigator for safety, behavioral, compliance, or administrative reasons.

If a participant does not return for a scheduled visit, every effort should be made to contact the participant's parent(s)/legal guardian(s). All attempts to contact the participant's parent(s)/legal guardian(s) and information received during contact attempts must be documented in the participant's source document. In any circumstance, every effort should be made to document participant outcome, if possible.

At the time of discontinuing, please refer to the investigator site file (ISF) and SoA for assessments to be collected at the time of study discontinuation and follow-up and for any further evaluations that need to be completed.

The participant's parent(s)/legal guardian(s) should ideally notify the investigator in writing of the decision to withdraw consent from future follow-up, whenever possible. The participant's parent(s)/legal guardian(s) should be questioned regarding their reason for withdrawal. The investigator or his or her designee should capture the reason for withdrawal in the CRF for all participants.

The participant should be requested to return for a final visit, if applicable, and the investigator will perform the procedures indicated for the next visit. Any AEs or SAEs that are continuing at the time of withdrawal from the study should be followed until resolution or, in case of permanent impairment, until the condition stabilizes.

A final telephone contact 6 months after vaccination ([Section 8.10.3](#)) for the collection of safety information should be completed for all participants who withdraw or who have been withdrawn after administration of investigational product, unless consent for further contact has been withdrawn, or the participant is lost to follow-up. Participant withdrawal should be explained in the source documents and should include whether the withdrawal is from study procedures and/or postvaccination study follow-up.

If a participant is withdrawn from the study, his/her parent(s)/legal guardian(s) may request destruction of any remaining samples, but data already generated from the samples will continue to be available, and may be used to protect the integrity of existing analyses. The investigator must document any such requests in the site study records.

If the participant is withdrawn from the study and his/her parent(s)/legal guardian(s) also withdraws consent for disclosure of future information, no further evaluations should be performed and no additional data should be collected. The sponsor may retain and continue to use any data collected before such withdrawal of consent.

When a participant is withdrawn from the study because of an SAE, the SAE must be recorded on the CRF and reported on the Vaccine SAE Reporting Form.

Lack of completion of all or any of the withdrawal/early termination procedures will not be viewed as protocol deviations so long as the participant's safety was preserved.

7.3. Lost to Follow-up

A participant will be considered lost to follow-up if he or she repeatedly fails to return for scheduled visits and the participant's parent(s)/legal guardian(s) is unable to be contacted by the study site.

The following actions must be taken if a participant fails to return to the clinic for a required study visit or fails to respond to the 6-month safety follow-up telephone call:

- The site must attempt to contact the participant's parent(s)/legal guardian(s) and reschedule the missed visit as soon as possible and counsel the participant's parent(s)/legal guardian(s) on the importance of maintaining the assigned visit schedule and ascertain whether or not the participant's parent(s)/legal guardian(s) wishes the participant to, and/or should, continue in the study;
- Before a participant is deemed lost to follow-up, the investigator or designee must make every effort to regain contact with the participant's parent(s)/legal guardian(s) (where possible, 3 telephone calls and, if necessary, a certified letter to the participant's last known mailing address or local equivalent methods). These contact attempts should be documented in the participant's medical record;
- Should the participant's parent(s)/legal guardian(s) continue to be unreachable, the participant will have been considered to have withdrawn from the study.

[figure not shown]
Discontinuation of specific sites or of the study as a whole is handled as part of [Appendix 1](#).

